## DOCUMENT HISTORY

Document	Date of Issue	Overall Rationale
Amendment 05	06-JUL-2022	To remove the dependency of enrollment of the second cohorts of Groups 2 and 3 on the availability of safety/tolerability data from Study MK-1986-018.
Amendment 04	01-JUN-2021	To clarify that participants can receive the oral suspension dose via feeding tube.
Amendment 03 (Ukraine only)	16-JAN-2020	To indicate that neither Ukraine nor Norway will enroll subjects in Groups 3 and 6 (preterm neonates).
Amendment 02	11-OCT-2019	To update the dose levels following the first interim analysis and to convert the second IV cohort of each neonatal group to receive multiple (not single) doses.
Amendment 01	13-SEP-2018	To ensure an adequate distribution of age and weight among subjects aged 28 days to <24 months, particularly among subjects aged 28 days to <6 months.
Original Protocol	23-JUN-2016	Not applicable

## **SUMMARY OF CHANGES**

### **PRIMARY REASON FOR THIS AMENDMENT:**

To remove the dependency of enrollment of the second cohorts of Groups 2 and 3 on the availability of safety/tolerability data from Study MK-1986-018.

Section Number	Section Title	Description of Change	Rationale
2.1	Trial Design	Removed dependency of enrollment of the second cohorts of Groups 2 and 3 on the availability of safety/tolerability data from Study MK-1986-018.	This contingency was initially in place to ensure that there was an understanding of the potential risks in neonates based on dosing in older subjects prior to initiating multiple dosing in neonates. From the review of all the available safety data from completed and ongoing single- and multiple-dose studies in pediatric subjects from birth to <18 years of age, tedizolid phosphate is generally well tolerated with no new safety concerns identified in the pediatric population and no age-related trends in tolerability. Therefore, this contingency is being removed and multiple dosing of neonates will be allowed to proceed.

### **ADDITIONAL CHANGES FOR THIS AMENDMENT:**

Section Numbers	Section Titles	Description of Changes	Rationale
1.0 5.10	Trial Summary Beginning and End of the Trial	Added text to specify the end of the study for purposes of analysis and reporting is the time when the Sponsor receives the last laboratory result or the time of final contact with the last participant, whichever comes last.	To define the end of the study for purposes of analysis and reporting.

Section Numbers	Section Titles	Description of Changes	Rationale
2.1	Trial Design	Changed all study design description text to future tense.	The trial design section should describe the plan; actual conduct and outcomes are described in Section 4, Background and Rationale.
4.2.2	Rationale for Dose Selection/Regimen/Modification	Added text to indicate that continuation at the initial planned dose levels were supported by interim analyses during the course of this study.	To clarify that the planned interim analyses during the course of the study have been conducted (and have supported continuation at the planned dose).
4.3	Benefit/Risk	Updated summary of pediatric safety data as of 21-APR-2022.	To add the most recent review of safety data in the pediatric population.
5.2	Trial Treatment(s)	The table of Trial Treatment (Table 2) was updated to add information for intervention type, dose formulation, unit dose strength, regimen, and sourcing.	To align with the Sponsor's current protocol standards.
Title Page Section 12.1 Throughout	Title Page Code of Conduct for Clinical Trials	Sponsor entity name and address change.	Merck Sharp & Dohme Corp. underwent a name and address change to Merck Sharp & Dohme LLC, Rahway, NJ, USA. This conversion resulted only in an entity name change and update to the address.
Section 12.1	Code of Conduct for Clinical Trials	Updates to the protocol template text.	To align with the current version of the Code of Conduct and other regulatory, ethical, and study governance requirements.

Section Numbers	Section Titles	Description of Changes	Rationale
Throughout Document		Minor administrative, formatting, grammatical, and/or typographical changes were made throughout the document.	To ensure clarity and accurate interpretation of the intent of the protocol.

## 1.0 TRIAL SUMMARY

Abbreviated Title	A Single- and Multiple-dose Study of Tedizolid Phosphate in Pediatric Subjects Aged <2 Years
Sponsor Product Identifiers	MK-1986 (tedizolid phosphate)
Trial Phase	Phase 1
Clinical Indication	Treatment or prophylaxis against gram-positive infections
Trial Type	Interventional
Type of control	Uncontrolled
Route of administration	Intravenous (Part A) and oral (as oral suspension; Part B)
Trial Blinding	Unblinded Open-label
Treatment Groups	
Part A:
 
Group 1 (N=10):
 

• Cohort 1 (n=4-6): MK-1986 IV single-dose given to pediatric subjects aged 28 days to <6 months

• Cohort 2 (n=4-6): MK-1986 IV single-dose given to pediatric subjects aged 6 months to <24 months

 
Group 2 (N=10):
 

• Cohort 1 (n=6): MK-1986 IV single-dose given to full-term neonates* aged birth to <28 days

• Cohort 2 (n=4): MK-1986 IV multiple-dose (twice daily for 3 days) given to full-term neonates* aged birth to <28 days

 
Group 3 (N=10):
 

• Cohort 1 (n=6): MK-1986 IV single-dose given to preterm neonates† aged birth to <28 days

• Cohort 2 (n=4): MK-1986 IV multiple-dose (twice daily for 3 days) given to preterm neonates† aged birth to <28 days

 
Part B:
 
Group 4 (N=4): MK-1986 oral suspension single-dose given to pediatric subjects aged 28 days to <24 months,
 
Group 5 (N=4): MK-1986 oral suspension single-dose given to full-term neonates* aged birth to <28 days, and
 
Group 6 (N=4): MK-1986 oral suspension single-dose given to preterm neonates† aged birth to <28 days
 
In subjects who receive multiple-dose study medication, tedizolid phosphate will be administered twice daily for 3 days.

	
* Full-term neonate is defined as an infant born <math>\geq 37^{\text{th}}</math> week of gestation.
 
† Preterm neonate is defined as a neonate born after completion of 26 weeks of gestation and before the beginning of the <math>37^{\text{th}}</math> week of gestation

Number of trial subjects	Approximately 42 subjects will be enrolled.
Estimated duration of trial	
The Sponsor estimates that the trial will require approximately 3 years from the time the documented informed consent is provided for the first subject until the last subject's last study-related phone call or visit.
 
For purposes of analysis and reporting, the overall study ends when the Sponsor receives the last laboratory result or at the time of final contact with the last participant, whichever comes last.

Duration of Participation	Each subject will participate in the trial for approximately 18-20 days from the time the parent, guardian, or legally acceptable representative provides the documented informed consent form (ICF) through the final contact (Day 14). After a screening phase of $\leq 4$ days, each subject will receive tedizolid phosphate as a single-dose or as multiple doses (twice daily for 3 days). After dosing is complete, each subject will be followed for 14 days for adverse events.

A list of abbreviations used in this document can be found in Section 12.4.

## 2.0 TRIAL DESIGN

### 2.1 Trial Design

This is a non-randomized, two-part, multisite, open-label trial to assess the safety and pharmacokinetics (PK) of tedizolid phosphate and its active metabolite tedizolid in hospitalized subjects (inpatients) aged  $<2$  years who are receiving prophylaxis or treatment for a confirmed or suspected infection with gram-positive bacteria, to be conducted in conformance with Good Clinical Practices.

Safety and PK will be assessed following administration of tedizolid phosphate IV (Part A) or oral suspension (Part B) to pediatric inpatients aged 28 days (subjects may be preterm or full-term at birth) to  $<6$  months, 6 months to  $<24$  months, and 28 days to  $<24$  months (Group 1 Cohort 1, Group 1 Cohort 2, and Group 4, respectively), full-term neonates aged birth to  $<28$  days (Groups 2 and 5, respectively), and preterm neonates aged birth to  $<28$  days (Groups 3 and 6, respectively). A full-term neonate is defined, in this study, as an infant born  $\geq 37^{\text{th}}$  week of gestation. A preterm neonate is defined, in this study, as a neonate born after completion of 26 weeks of gestation and before the beginning of the  $37^{\text{th}}$  week of gestation.

Study progression to younger subjects will occur as follows: Group 1 Cohort 1 (IV, aged 28 days to  $<6$  months) and Group 1 Cohort 2 (IV, aged 6 months to  $<24$  months) will initiate enrollment first, at a dose of 3 mg/kg, based on the interim results of a separate PK and tolerability study in children aged 2 to  $<12$  years, MK-1986-013 (TR701-120). To ensure adequate representation of age and weight within the 28 days to  $<24$  months age range, a minimum of 2 subjects each will be enrolled into Group 1 Cohorts 1 and 2 prior to the first

interim assessment. After the first 5 subjects are enrolled in Group 1 (Cohorts 1 and 2 combined), an interim assessment of PK from this study (MK-1986-014) will be performed to determine whether the dose required adjustment.

After dose adjustment based on the first interim assessment, Group 1 Cohorts 1 and 2 will continue enrolling until complete; then Group 4 (aged 28 days to <2 years, receiving oral suspension) will enroll. In parallel, the first cohorts of Groups 2 and 3 (single-dose IV, full-term and preterm neonatal age groups) will begin enrollment at the planned starting dose of 3.0 mg/kg (body weight <10 kg) or 2.5 mg/kg (body weight 10 to <30 kg). After 6 subjects each are enrolled in the first cohorts of Groups 2 and 3, separate interim assessments will be performed for a potential dose adjustment. Enrollment of the second cohorts of Groups 2 and 3 (multiple-dose tedizolid phosphate) will occur only after these separate interim assessments.

Note, as of Amendment 05, these assessments have been completed, and enrollment of the second cohorts of Groups 2 and 3 (multiple-dose IV, full-term and preterm neonatal groups) will be initiated, supported by the safety profile observed across all age groups in studies MK-1986-014 and MK-1986-018.

Along with the second cohorts of Groups 2 and 3, Groups 5 and 6 will open for enrollment. Given the high bioavailability of tedizolid (approximately 90%) expected based on data from adults and older children, the oral suspension treatment will be administered at the dose selected based on the interim IV PK data. No interim analyses are planned for Part B (oral suspension) because of the small size of the oral groups.

Each of the IV groups (Group 1 [Cohorts 1 and 2 combined], Group 2 [Cohorts 1 and 2 combined], and Group 3 [Cohorts 1 and 2 combined]) will contain at least 10 subjects, with interleaved PK sampling such that data from all timepoints are obtained but no single subject provides more than 3 PK samples, to ensure total blood collection volume is within a safe range for the age group. Similarly, the oral groups (Groups 4, 5, and 6) will each have at least 4 subjects, again with interleaved PK sampling. Because of the relatively sparse nature of the sampling, subjects may be replaced if they are missing >1 PK sample (see Section 5.9).

[figure not shown]
Further local restrictions on cohort opening may be applied based on country-specific requirements or site constraints.

Specific procedures to be performed during the trial, as well as their prescribed times and associated visit windows, are outlined in the Trial Flow Chart - Section 6.0. Details of each procedure are provided in Section 7.0 – Trial Procedures.

## 2.2 Trial Diagram

The trial design is depicted in [Figure 1](#).

Figure 1 Schematic of Study Design for Study MK-1986-014 (TR701-121)

IV=intravenously; MD=multiple-dose (twice daily for 3 days); PK=pharmacokinetics; PO=orally; SD=single-dose

Note: With the exception of the first 5 subjects in Group 1 (3 mg/kg single-dose), subjects in the study will receive body weight-based doses of tedizolid phosphate, as follows: <10 kg - 3.0 mg/kg tedizolid phosphate; 10 to <30 kg - 2.5 mg/kg tedizolid phosphate (see Section 5.2). This may be modified further after additional interim analyses.

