#### **4.1.1 Pharmaceutical and Therapeutic Background**

Tedizolid phosphate (SIVEXTRO®, MK-1986) is a novel oxazolidinone prodrug antibiotic that is rapidly converted in vivo by phosphatases to the microbiologically active moiety tedizolid. Tedizolid is a protein synthesis inhibitor that interacts with the 50S subunit of the bacterial ribosome. Tedizolid has bacteriostatic activity against gram-positive bacteria including common skin pathogens *Staphylococcus aureus* (both methicillin-sensitive and –resistant strains) and *Streptococcus pyogenes*, less common species causing acute bacterial skin and skin structure infections (ABSSSI), *S. anginosus*-milleri group and *Enterococcus faecalis*, and other gram-positive aerobes and anaerobes. The tablet is highly (~90%) bioavailable after oral dosing in adults, and is provided in both IV and oral formulations. Following oral administration of a single 200 mg dose to healthy adults, maximal plasma concentrations of tedizolid (approximately 2 µg/mL) are achieved approximately 3 hours after dosing when fasted; Tmax is delayed by approximately 6 hours when tedizolid phosphate is dosed with a meal; however, the AUC is unaffected by administration with or without food. Conversion of the prodrug tedizolid phosphate to the active metabolite, tedizolid, is extremely rapid, with a half-life of 10 minutes. When the drug is dosed IV, exposure peaks at the end of the 60-minute infusion period. Systemic prodrug is rarely detectable after oral dosing. The terminal half-life of tedizolid elimination is 12 hours. Exposure is generally dose-proportional in humans.

Tedizolid phosphate is approved for the treatment of ABSSSI in adults in multiple regions, including the United States and European Union (EU), but its safety and effectiveness have not been established in children and adolescents.

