Following enrollment of the first 5 subjects in Group 1, the pediatric population PK model was updated to include these data, as well as the PK data from the recently completed Studies MK-1986-012 and MK-1986-013 and an adolescent PK study, TR701-111. The updated model indicates that the weight-based tedizolid phosphate dose predicted to provide the closest approximation to adult exposure (as AUC and  $C_{max}$ ) should be based on body weight range, with infants <10 kg receiving 3 mg/kg and children 10 to <30 kg receiving 2.5 mg/kg. Additional interim analyses of the neonatal single-dose IV cohorts have supported continuation of the study at these dose levels. In a multiple-dose setting, these doses would be given twice daily to achieve an AUC similar to that in adults at the approved dose, and likewise provide a high probability of target attainment (>99%) at the breakpoint MIC of 0.5 mg/L.

The addition of multiple-dose arms in this study allows for the collection of multiple-dose PK and safety data in full-term and preterm neonates, which will be difficult to obtain in treatment studies given the low incidence of ABSSSI in newborns.

Further dose modification may occur during the course of this study following review of additional interim data.

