#### **4.2.2.2 Starting Dose for This Trial**

It was planned that subjects would receive a single dose of 3 mg/kg of tedizolid phosphate as either an IV infusion (Part A) or oral suspension (Part B). This dose was adjusted in Amendment 01, prior to the start of the study, from the single-dose of 5 mg/kg that was planned in the Initial Protocol. This dose adjustment was based on interim analyses of PK data from Study MK-1986-013 (see Section 4.2.2). Following the first interim analysis of the first 5 subjects enrolled in study MK-1986-014, the starting doses for the neonatal age groups have been further updated at Amendment 02 to 3.0 mg/kg (body weight <10 kg, which will span the entire neonatal age group).

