#### Exploratory Endpoints

Pharmacokinetics: bioavailability of tedizolid following administration of tedizolid phosphate oral suspension (Part B, Groups 4, 5 and 6).

The PK parameters are defined as follows:

AUC 0-last	Area under the concentration-time curve from time 0 to time of last quantifiable drug concentration
AUC 0-∞	Area under the concentration-time curve from time 0 extrapolated to infinity
CL or CL/F	Total body clearance or apparent total body clearance
Vd or Vd/F	Volume of distribution or apparent volume of distribution
C max	Maximum concentration
T max	Time to reach C max
t 1/2	(Apparent terminal) Half-life
%BA	Percent bioavailability (oral only) calculated as (individual AUC 0-inf PO * dose IV) / (mean AUC 0-inf IV * dose PO) (for similar collection scheme), and overall for mean across both collection schemes, within and across all age groups

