### **IV Administration (Group 1 [Cohort 1 and 2 Combined], Group 2, and 3)**

A non-model-based GM of the AUC and  $C_{max}$  of tedizolid phosphate and its active metabolite, tedizolid after administration (5th dose or first dose on Day 3 for multiple-dose groups) will be calculated for each PK sampling scheme by age and dose (if dose adjusted at interim analysis) group. A ratio of non-model based GM between two PK sampling schemes will also be calculated by age group. If the ratio is greater than 2.0 or less than 0.5 for an age group, the naïve-pooled approach will be used to summarize the PK. In this approach, only one value for each PK parameter will be estimated for each age group, as specified in Section 7.1.3.2.1. If the ratio of non-model based GM between two PK sampling schemes is within 0.5 and 2.0 for an age group, individual PK parameter values will be estimated. An ANOVA model including factor for Group/Cohort will be used to analyze log transformed PK parameter values of tedizolid phosphate and tedizolid. Point estimates and two-sided 95% confidence intervals will be constructed for the GM in pediatric subjects, by age group, for AUC and  $C_{max}$  of tedizolid phosphate and tedizolid.

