### **Oral Administration (Groups 4, 5, and 6)**

The AUC of tedizolid phosphate and tedizolid, administered as oral suspension will be calculated using naïve-pooled approach as specified in Section 7.1.3.2.1. Only one value for AUC will be estimated for each age group.

The bioavailability will be estimated by dividing the naïve-pooled AUC from oral administrated subjects by the estimated AUC from IV administrated subjects, for each age

group. If the ratio of non-model-based GM between two PK sampling schemes is between 0.5 and 2.0, then GM AUC estimate from ANOVA model will be used as the estimated AUC from IV administrated subjects. Otherwise, the naïve-pooled AUC estimate from each age group will be used. An average bioavailability will also be reported across age groups.

For IV administrated subjects with available individual PK parameter estimates, individual values will be listed for each PK parameter by age group, dose and PK sampling scheme, and the following (non-model-based) descriptive statistics will be provided: N (number of subjects with non-missing data), arithmetic mean, standard deviation, arithmetic percent CV (calculated as  $100 \times \text{standard deviation}/\text{arithmetic mean}$ ), median, minimum, maximum, GM, and geometric percent CV (calculated as  $100 \times \text{sqrt}[\exp(s^2) - 1]$ , where  $s^2$  is the observed variance on the natural log-scale).

The effects of body weight and renal function on the PK parameter values may be graphically analyzed if appropriate. These data may be used in a population PK analysis.

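### The Section 8.2.4.3 bioavailability ratio has no dose term and conflicts with the dose-scaled definition in Section 8.2.2; the Group 1 ANOVA mean also ignores dose

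*Combined protocol and SAP*

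**What the plan says.** **Dosing.** Section 2.2 says "With the exception of the first 5 subjects in Group 1 (3 mg/kg single-dose), subjects in the study will receive body weight-based doses", and gives the bands as "<10 kg - 3.0 mg/kg tedizolid phosphate; 10 to <30 kg - 2.5 mg/kg tedizolid phosphate". Group 1 (IV, planned N=10) thus has five subjects dosed at 3 mg/kg whatever their weight and the rest dosed by band. Group 4 (oral, N=4, same age range) is dosed by band throughout. The neonatal groups do not mix doses: Section 4.2.2.2 sets "3.0 mg/kg (body weight <10 kg, which will span the entire neonatal age group".

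**IV analysis.** In Section 8.2.4.3 the first-step geometric means are split by sampling scheme, age and, if it was adjusted, dose. Individual values are listed by dose as well. The model step drops dose: "An ANOVA model including factor for Group/Cohort will be used to analyze log transformed PK parameter values of tedizolid phosphate and tedizolid". No dose-normalised parameter is mentioned there or in Section 8.1.1.2.

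**Bioavailability.** There are three statements:
- Sections 8.1.1.2 and 8.2.4.3: "The bioavailability will be estimated by dividing the naïve-pooled AUC from oral administrated subjects by the estimated AUC from IV administrated subjects", by age group. The IV term is the ANOVA geometric mean if the two sampling schemes agree within a factor of 2, and otherwise the naïve-pooled AUC.
- Section 8.2.2: "Percent bioavailability (oral only) calculated as" individual oral AUC times IV dose, over mean IV AUC times oral dose.
- Section 7.1.3.2.1: IV AUC over oral AUC, with no dose term.

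Sections 7.1.3.2.1, 8.1.1.2 and 8.2.4.3 allow only a naïve-pooled analysis for Groups 4 to 6, so each oral group has one AUC.

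**The concern.** The methods text can be run as written and the endpoint definition cannot, because it needs individual oral AUCs. An analyst is likely to follow the methods text, and the dose term is then lost. Any difference in dose mix between Group 4 and Group 1 would appear as a difference in bioavailability. When the weight mix is equal, the error runs essentially one way: heavier subjects among the first five received more than their later band, so the IV denominator is raised and bioavailability is understated.

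The denominator is normally the Group 1 ANOVA geometric mean, so the missing dose term there matters twice: in the bioavailability ratio, which is exploratory, and in the Group 1 AUC and Cmax estimates, which belong to the first primary objective.

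**Working it through.** **Inputs.** Doses 3.0 and 2.5 mg/kg, ratio 1.20 (Section 2.2). Group 1 N=10 and Group 4 N=4 (Section 5.3). At least 2 subjects in each Group 1 cohort before the interim at 5 subjects (Section 2.1), so at most 3 of the first five are in Cohort 2. Between-subject SD of log AUC 0.27 for tedizolid phosphate and 0.32 for tedizolid (Section 8.2.7). Expected bioavailability about 0.90 (Section 2.1). Proportionality: "Exposure is generally dose-proportional in humans" (Section 4.1.1).

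**Assumptions.** AUC is proportional to mg/kg dose. Cohort 1 infants (under 6 months) weigh less than 10 kg. Let k be the number of first-five subjects of 10 kg or more. Weights are not given, so k is taken as 0 to 3.

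**1. The plan's own figure.** The probability that the 95% CI stays within 60% to 140% of the geometric mean is P[χ²(n−1) ≤ (n−1)(ln 1.4·√n/(t·SD))²].
- n=10: t=2.262 gives 99.9% and 97.8% (plan: 99% and 97%).
- n=6: t=2.571 gives 78.3% and 58.7% (plan: 78% and 58%).

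The planning figures reproduce. With five subjects at each dose, the n=10 values become 99.6% and 96.3%, so precision is not the issue.

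**2. Group 1 geometric mean.** Relative to the weight-banded regimen, the factor is 1.20^(k/10).

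| k | Factor | Shift |
|---|---|---|
| 0 | 1.000 | 0% |
| 1 | 1.018 | 1.8% |
| 2 | 1.037 | 3.7% |
| 3 | 1.056 | 5.6% |

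If the Cohort 1 assumption is dropped and all five weighed 10 kg or more, the shift is 1.20^0.5 = 1.095, or 9.5%.

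**3. Unscaled Group 4 / Group 1 ratio.** The naïve-pooled oral profile averages concentrations arithmetically and the IV term is geometric. The ratio therefore reads 0.90 × (arithmetic mean oral dose)/(geometric mean IV dose). This isolates dose and ignores other differences between the two kinds of mean.

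| Case | Mean oral dose | Geometric mean IV dose | Reads |
|---|---|---|---|
| Half of each group ≥10 kg, k=0 | 2.75 | 2.739 | 0.904 |
| Half of each group ≥10 kg, k=3 | 2.75 | 2.893 | 0.856 |
| 80% of each group ≥10 kg, k=3 | 2.60 | 2.739 | 0.854 |
| Extreme: oral all 2.5, IV all 3.0 | 2.50 | 3.000 | 0.750 |
| Extreme: oral all 3.0, five of ten IV at 2.5 | 3.00 | 2.739 | 0.986 |

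Five is the most Group 1 subjects that can be at 2.5 mg/kg with N=10, because the first five all received 3 mg/kg. Dividing by dose first returns about 0.90 in every row.

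**4. Sensitivity to the proportionality assumption.** Suppose instead that the bands give equal AUC at all weights, as Section 4.2.2 intends. Only the k subjects then distort the ratio: 0.90/1.20^(k/10) = 0.900, 0.884, 0.868, 0.852. The 0.85 to 0.90 range survives; the wider extremes do not arise.

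**5. Inverse formula.** Read literally, Section 7.1.3.2.1 would report 1/0.90 = 1.11.

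**The case against.** A reader might infer that the Group 1 mean and the Group 4 ratio describe no single regimen. The documents do not support that. Section 4.2.2 explains that dosing "should be based on body weight range, with infants <10 kg receiving 3 mg/kg and children 10 to <30 kg receiving 2.5 mg/kg"; two mg/kg values across weight bands are one regimen, and Group 4 follows it throughout. Only first-five subjects of 10 kg or more depart from it, and there may be none.

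A reader might also infer that the plan has no dose normalisation for bioavailability. Section 8.2.2 has it. The defect is a conflict between sections, not a plain omission.

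Dose is also partly handled elsewhere: the non-model geometric means and the listings are kept by dose, body-weight effects may be plotted, and a population PK analysis is allowed. That stands, but none of it corrects the ANOVA mean or the ratio built on it.

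The shift is small beside sampling error. With SD 0.32 and n=10 the 95% CI runs from exp(−0.229) to exp(0.229), about −20% to +26%, in a descriptive study without hypothesis tests. This also stands and limits the importance of the point.

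A larger figure can be obtained for Cohort 2 alone: 1.20^(3/4) = 1.147, or 14.7%, with n=4. But Section 5.3 splits Group 1 for enrolment only, and the objective and the Section 8.2.4.3 heading combine the cohorts. Only the Group/Cohort wording in Section 8.1.1.2 hints at a separate estimate.

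**Conclusion.** The point holds as a minor one. The plan gives three incompatible bioavailability formulas. The one that can be run as written oral over IV omits dose, although Groups 1 and 4 can differ in dose mix. Against a true 0.90 it reads about 0.85 to 0.90 with equal weight mix and k from 0 to 3, and 0.75 to 0.99 at the extremes. The extremes are bounds, not expectations, and they also require AUC per mg/kg not to vary with weight. The Group 1 ANOVA geometric mean is raised by 0% to 5.6% relative to the weight-banded regimen under the same assumption on k.

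Groups 5 and 6 are not affected by dose mix, since neonates are all in the 3.0 mg/kg band, but the formula conflict covers them too. The planned average across age groups would inherit the Group 4 error in diluted form. Nothing here bears on which dose is right.

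**What to change.** 1. Define bioavailability once, as dose-normalised oral AUC over dose-normalised IV AUC. Divide each subject's concentrations or AUC by the actual mg/kg dose before naïve pooling and before forming the IV geometric mean used as denominator.
2. Reconcile Sections 7.1.3.2.1, 8.1.1.2, 8.2.2 and 8.2.4.3 to that definition. This means correcting the inverted ratio and removing the need for individual oral AUCs in Section 8.2.2.
3. For Group 1, also report the ANOVA geometric means of AUC and Cmax on values scaled to the weight-band dose (value × band mg/kg ÷ actual mg/kg). Keep the unscaled results and the listings by dose.

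**Cost.** A few sentences across four sections. No new data are needed, since individual doses and screening weights are recorded.

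**Downside.** The scaling relies on dose-proportionality, which Section 4.1.1 states only in general for humans. Dividing by mg/kg also does not remove any dependence of AUC per mg/kg on weight: if the bands equalise exposure, and all oral subjects were at 2.5 and all IV subjects under 10 kg at 3.0, the scaled ratio would read 0.90 × 1.20 = 1.08. The weight mix of both groups should therefore be shown beside the ratio, with a sensitivity ratio that uses the item 3 geometric mean and the oral AUC unscaled.
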